[figure not shown]

Perceptual-motor Interaction to Improve Bimanual Coordination After Stroke

NCT03755076

Date: 6-18-2025

CONSORT Flow Diagram

Study protocol:

Specific Aim: Determine the immediate effects of perceptual cues on bimanual coordination in stroke survivors. This aim was to determine the immediate effect of perceptual cues providing feedback about (a) between-limb coordination and (b) differential weighting of the two arms on spatial and temporal measures of bimanual coordination during a common goal bimanual reaching task.

Hypotheses: (a) Feedback on the relative timing between arms (i.e., between limb coordination), provided in the form of a horizontal tilt of the virtual brick, will shorten the time lag and increase CCr over practice. (b) A greater weighting coefficient applied to the weaker arm along with feedback of relative timing between arms (i.e., both cues) may transiently impair temporal and spatial bimanual coordination measures but will improve over practice.

Rationale: Perceptual cueing has a strong effect on motor performance. The requirement to minimize the tilt of the brick will reduce redundancy by constraining the two arms to move simultaneously, thus improving the coordination between arms. In addition to the tilt, when each arm is differentially weighted, a greater movement of the paretic arm is required to move the virtual brick to the target window. However, this requires the paretic arm to move farther and faster than the non-paretic arm to ensure that the brick is moved horizontally to the target. These differential demands on each arm may impair temporal and spatial coordination measures early after the introduction of differential arm-weighting cues. However, as evident from our preliminary data, patients will improve their spatial and temporal coordination with more trials.

Participants: A total of 184 potential participants were screened and seventy nine participants were included in the study. These consisted of fifty individuals with chronic (> 6 months since stroke) hemiparesis following unilateral cortical or subcortical stroke and twenty-nine age-matched controls. An equal number of patients with left- and right-sided brain damage were recruited. The inclusion criteria were as follows: (a) ability to reach

along a diagonal direction at least 80% of their arm length while fully supported on a frictionless surface and trunk constrained. Our previous experience suggested that this performance criterion will recruit a relatively large spectrum of severity from mild to moderate impairments (Fugl-Meyer (FM) scores 32-66). Although this excluded patients with more severe impairments, such as those with complete paralysis, it is now known that different stroke severities require distinct treatment approaches. In addition, patients with severe motor impairments may not be able to engage their arms in bimanual or unimanual activities, thus limiting the testing of coordination. Patients with very mild impairments (FM 60-66) will be included because they may have higher-order coordination deficits due to lesions in brain regions crucial for planning and coordinating bimanual actions. (b) Mini-mental scale score > 26, (c) score of 4 or above on the auditory verbal comprehension part of the Western Aphasia Battery to ensure intact comprehension and following commands, and (d) no evidence of hemispatial neglect tested by a line bisection test. (e) No contraindications to TMS or MRI. Attempts were made to include as many men and women as possible. The exclusion criteria were as follows: bilateral stroke, complete paralysis, basal ganglia/cerebellar stroke, pain or stiffness in the upper extremity that would interfere with the task, or inability to follow task instructions.

Procedure: Participants were instructed to “move” a common virtual brick with both arms to a target window without tilting the brick within a target MT of 1.2 seconds. Participants completed four 60-trial blocks in pseudorandom order. Each block consisted of a distinct task condition depending on the nature of the perceptual cues provided. The conditions were:

Condition 1: Indiscriminate: Participants transported a common virtual brick fixed in a no-tilt position to the target position in a pseudorandom order. The movement of the brick in the X and Y axis is an unweighted average of the two arm movements, that is, each arm contributes to 50% of the virtual bar movement (50-50 weighting). Thus, the feedback cue was indiscriminate (i.e., just the movement of the brick without any additional information about the relative time lag or differential weighting).

Condition 2: Altered gain: This was similar Condition 1 (virtual brick fixed in no-tilt), but the arm weighting will be such that the gain of the paretic arm was reduced. With this manipulation, a farther movement of the paretic arm was required to maintain its contribution. Thus, the only perceptual cue provided here was related to the differential weighting of the paretic arm.

Condition 3: Coordination: For Condition 3, the weighting coefficients of the two arms were equal (i.e. 50-50); and the virtual brick tilted in the direction of the lagging arm proportional to the relative time lag between the arms. Thus, the only perceptual cue provided was the relative time lag between the arms. *Operational definition of relative time lag:* Relative time lag is different from the absolute time lag. The relative time lag is the time lag between the relative timings of each arm within its trajectory. To illustrate, if the left and right arms contribute to 70 and 30% of the brick movement, respectively, the relative time lag at mid-movement will be zero if the left and right arms have covered half of their respective trajectories. Therefore, the relative time lag is influenced by the temporal and spatial components of the movement of each arm. Concurrent and post-response feedback regarding the tilt and path of the virtual brick was provided after each trial.

Condition 4: Dual cues: In addition to the “tilt” feedback about the relative time lag (like in Condition 3), each arm was differentially weighted, that is, the paretic arm had a lower gain (or higher weighting coefficient) than the nonparetic arm (like Condition 2). Specifically, based on our preliminary studies, the lower gain the paretic arm contributed to ~60-70% of the virtual brick movement, whereas the nonparetic arm contributed to ~30-40% of the virtual brick movement. Thus, in this condition, participants received both perceptual conditions (relative time lag and differential weighting) simultaneously.

Dependent measures Coordination between the two arms was quantified by cross-correlation between the tangential velocities of the two arms. Spatial coordination was characterized by the peak cross-correlation coefficient (CCr) between the tangential velocity profiles of the two arms. CCr values closer to 1 indicated better spatial coordination. Temporal coordination was quantified as the time lag at which the peak

cross-correlation coefficient was obtained via cross-correlation analysis. A shorter time lag (closer to zero) indicated stronger temporal bimanual synchrony. A positive lag indicated that the paretic arm (non-dominant in the control) lagged behind the non-paretic arm (dominant in controls).

Statistical plan: The study design included between-subject variables (stroke and control groups) and two within-subject variables (perceptual cue conditions: 1-4; and two time points: start of practice (SOP) and end of practice (EOP). Z-score (Fisher's z)-transformed cross-correlation coefficients (CCrs) were used for analyses. Box-cox transformation was used for the time-lag data. Transformed measures of spatial and temporal coordination measures were analyzed using a separate 2 GROUP (stroke, controls) \times 4 PERCEPTUAL CUE CONDITIONS (veridical, coordination, altered gain, and combined coordination+ altered gain feedback) \times TIME (SOP, EOP) with repeated measures on the last two factors. The focus of this study was to compare the effects of different perceptual cues on individuals with stroke and age-matched neurotypical controls. Sex was used as the covariate.

Expected results and interpretation: We expected to observe a significant group main effect and a significant interaction between feedback and arm weighting. When the brick is fixed, we expect that there will be no difference in the arm weighting conditions; when the brick is free to tilt, we expect that 50-50 arm weighting will result in better temporal and spatial coordination compared to 70-30 arm weighting. Similarly, we expected poorer coordination for parallel conditions compared to the mirror condition. 70-30 arm weighting will lead to a greater contribution of the paretic arm than the 50-50 weighting.

Pitfalls and contingencies: It is likely that the tilt cue conveys spatial rather than temporal information. In such cases, we reiterate our instructions assisted by example templates of how the tilt is determined. We ensured that the participants' understanding was clear.

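### Controls were age-matched, but the GROUP x CUE x TIME model adjusts only for sex, so the matching variable is left out of the analysis

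*Combined protocol and SAP*

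**What the plan says.** Under Participants, "seventy nine participants were included in the study": "fifty individuals with chronic (> 6 months since stroke) hemiparesis" and "twenty-nine age-matched controls". The text does not say whether matching was individual or by frequency, at what ratio or within what tolerance, and it gives no age distribution for either group.

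Under Statistical plan, each transformed outcome (Fisher z of the cross-correlation coefficient; Box-Cox of the time lag) goes into a GROUP x CUE x TIME model "with repeated measures on the last two factors". GROUP is therefore the only between-subject factor. The covariate statement reads "Sex was used as the covariate"; age is not mentioned as a model term. The same section gives the study's focus as being to "compare the effects of different perceptual cues on individuals with stroke and age-matched neurotypical controls". The Expected results section adds "We expected to observe a significant group main effect".

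**The concern.** Stroke status is not randomised, so the GROUP contrast is observational and depends on the two groups being comparable. The investigators thought age important enough to govern the choice of controls. Ordinarily a variable that shapes the design is carried into the model, for two reasons.

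- **Precision and error rate.** Matching takes age variation out of the difference in group means. If age is not in the model, that variation stays in the error term. The standard error is then too large for the contrast it describes, and the test falls below its nominal level.
- **Protection.** If matching was loose, an age term removes the part of the group difference that is due to age. Without it, nothing in the analysis does so.

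At stake are the GROUP main effect, which the plan expects to be significant, and possibly the interactions with GROUP, which carry the comparison that the plan calls its focus.

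**Working it through.** **Inputs from the documents.** 50 stroke participants and 29 controls; 50 + 29 = 79, which agrees with the stated total. The covariate is sex. No alpha, power, effect size or SD is given, so there is no design calculation to reproduce.

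**Assumptions, none from the documents.** Within-group correlation ρ between age and the transformed outcome of 0.1 to 0.5; two-sided alpha 0.05; 80% power; outcome in SD units, taken as one between-subject value per person. Sex is left out of the illustration for simplicity.

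**Step 1: degrees of freedom.** 79 − 1 (intercept) − 1 (GROUP) − 1 (sex) = 76 between-subject error df. Adding age leaves 75.

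**Step 2: precision if mean age is balanced.** Adding age multiplies the residual variance by 1 − ρ². The unadjusted SE of the group difference is √(1/50 + 1/29) = 0.233 SD. The detectable difference is (1.960 + 0.842) × 0.233 × √(1 − ρ²), where the last factor is 1 without age. Without age it is 0.654 SD, and power at a true difference of 0.65 SD is 79.5%.

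| ρ | Variance removed (ρ²) | Detectable difference with age | Power at 0.65 SD with age |
|---|---|---|---|
| 0.1 | 1% | 0.651 | 79.9% |
| 0.2 | 4% | 0.641 | 81.1% |
| 0.3 | 9% | 0.624 | 83.1% |
| 0.4 | 16% | 0.599 | 86.0% |
| 0.5 | 25% | 0.566 | 89.5% |

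These figures do not count the loss of one df in 76, which is about 1% and cancels the gain at ρ = 0.1.

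**Step 3: type I error if mean age is exactly balanced.** The unadjusted statistic has SD of about √(1 − ρ²), so its true level is roughly 2 × [1 − Φ(1.96/√(1 − ρ²))].

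- ρ = 0.3: 1.96/0.954 = 2.055, giving 4.0%. Simulation with 10,000 runs gave 3.7% without age and 4.8% with it.
- ρ = 0.5: 1.96/0.866 = 2.263, giving 2.4%. Simulation gave 2.4% without age and 4.7% with it.

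**Step 4: bias if an age difference remains.** Bias in the GROUP effect = ρ × (age difference in SD).

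- A difference of 0.25 SD gives 0.025 (ρ = 0.1) to 0.125 SD (ρ = 0.5). Simulated unadjusted type I error was 5.2% at ρ = 0.3 and 5.3% at ρ = 0.5: the bias and the oversized SE roughly offset each other.
- A difference of 0.5 SD gives 0.05 to 0.25 SD. Simulated unadjusted type I error was 8.1% at ρ = 0.3 and 15.8% at ρ = 0.5, against about 5% with age in the model.

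**Step 5: the within-subject terms.** CUE and TIME contrasts are differences within a person. An age effect that is the same in every condition and at both time points cancels. GROUP x CUE or GROUP x TIME is biased only if an age difference remains and age also changes the response to cues or practice. The documents give nothing from which to size that.

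**The case against.** The strongest reply is that age was dealt with in the design. Controls were matched on age and sex was not described as matched, so matching on one and adjusting for the other is a coherent division of labour. This stands against any reading that the plan ignores age. It does not show that age should be left out of the model, because successful matching is the case in which omission makes the test conservative (Step 3).

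Three stronger readings are tempting but not supported.

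- A reader might infer from 50 against 29 that matching failed, since 50 − 29 = 21 patients could not have a control of their own. The documents never claim one-to-one matching. Frequency matching needs no pairs, and at 50/29 = 1.72 to 1 a variable ratio could cover everyone. The head count shows only that the method needs describing.
- A reader might take 0.233 SD as the age gap to expect. That is the chance SE for two unmatched samples, and matching is meant to do better. Chance imbalance of that kind is also already reflected in the unadjusted SE.
- A reader might conclude that the cue comparisons are biased. Both hypotheses concern change over practice, the aim concerns stroke survivors, and an additive age effect drops out of those contrasts.

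It also stands that the gain is small if age is weakly related to the outcome, and that the document is written largely in the past tense, so an age term added now may be post hoc. That affects how the analysis is labelled, not whether it is useful.

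**Conclusion.** The point holds as a matter of precision and error rate, with a conditional question of bias. The model omits the variable on which controls were matched, without explanation.

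If matching balanced age, the GROUP test is valid but conservative, with a true level of about 4% at ρ = 0.3 and 2.4% at ρ = 0.5. Between 1% and 25% of its residual variance could be removed over ρ = 0.1 to 0.5, and the benefit is negligible at the low end. If age still differs between groups, the GROUP effect is biased by ρ times the difference. The documents neither show nor rule out such a difference, so bias is a possibility to be checked and not a finding. The interactions with GROUP are exposed only under the further condition in Step 5.

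Every value of ρ and of residual imbalance here is an assumption. That age is on record is inferred from the matching, which could not be done without it.

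**What to change.** 1. Add mean-centred age beside sex as a between-subject covariate. This costs 1 of about 76 df and needs no new data, so it is a free improvement.
2. Add age x CUE, age x TIME and age x CUE x TIME, so that every interaction with GROUP is adjusted as well. These cost 3, 1 and 3 within-subject df: a small price, but not nothing.
3. State how controls were matched (individual or frequency, ratio, tolerance) and report the age distribution in each group.
4. If the analysis has already been run, keep the sex-adjusted model as specified and report the above as an age-adjusted sensitivity analysis, labelled as such.

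### The model has no block-position term, so practice or fatigue across the four cue blocks would cost the cue contrasts precision; bias cannot be ruled out while the order scheme is undefined

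*Combined protocol and SAP*

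**What the plan says.** The Procedure section states that "Participants completed four 60-trial blocks in pseudorandom order" and that "Each block consisted of a distinct task condition depending on the nature of the perceptual cues provided". Condition and block are therefore the same unit within a participant, and only the order scheme separates condition from position. Pseudorandom is not explained: no counterbalancing, constraint, stratification by group or washout is described. The instruction common to all blocks is to move "a common virtual brick with both arms to a target window without tilting the brick within a target MT of 1.2 seconds", although Conditions 1 and 2 fix the brick so that it cannot tilt.

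The Statistical plan has stroke and control groups between subjects and "two within-subject variables (perceptual cue conditions: 1-4; and two time points: start of practice (SOP) and end of practice (EOP"). The model crosses GROUP, CUE and TIME, with repeated measures on the last two. The only other term is given by "Sex was used as the covariate". The stated aim of the analysis is: "The focus of this study was to compare the effects of different perceptual cues on individuals with stroke and age-matched neurotypical controls". Hypothesis (a), by contrast, concerns change within practice: timing feedback "will shorten the time lag and increase CCr over practice".

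**The concern.** Four blocks of 60 trials make 240 trials of closely related reaching. Some learning or fatigue from one block to the next is plausible, particularly in stroke participants spanning a "relatively large spectrum of severity from mild to moderate impairments". The documents neither state nor size such an effect.

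If it exists and is not modelled, a participant's Condition 3 minus Condition 1 difference contains the true cue effect plus the effect of having done the two conditions at different positions. Randomising order makes that second part average to zero over participants. It does not take its variance out of the error term.

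The contrasts exposed are those between conditions and their stroke-control differences. These are the stated focus of the analysis, and they include the 50-50 versus 70-30 difference anticipated under Expected results.

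**Working it through.** The plan has no power calculation, SD, effect size or practice size, so there is no figure of its own to reproduce.

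**Inputs from the documents:** 50 stroke, 29 controls, four blocks per participant.

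**Assumed, on the transformed outcome scale:** block-mean within-participant SD 0.5 (variance 0.25); Condition 3 minus 1 effect in stroke 0.28; stroke-minus-control difference in that effect 0.47. The two effects were chosen to give about 80% power without practice effects.

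**Step 1: variance added.** With positions 1 to 4 in random order, each position has variance (16 - 1)/12 = 1.25. The covariance between the positions of two conditions is -1.25/3. The position difference has variance 2(1.25) + 2(1.25)/3 = 10/3. A shift of delta per block adds (10/3)*delta^2 to the variance of a two-condition difference, or (5/3)*delta^2 per block.

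**Step 2: planned power, stroke contrast.** SE = sqrt(2*(0.25 + (5/3)*delta^2)/50). Error df = 316 - 79 - 6 = 231: 79 x 4 block means, less 79 participant means and three cue effects in each of two groups.

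| delta per block | error variance | SE | power, effect 0.28 | power, effect 0.40 |
|---|---|---|---|---|
| 0 | 0.250 | 0.100 | 79.6% | 97.8% |
| 0.05 | 0.254 | 0.101 | 79.0% | 97.7% |
| 0.1 | 0.267 | 0.103 | 77.0% | 97.1% |
| 0.2 | 0.317 | 0.113 | 69.8% | 94.3% |
| 0.3 | 0.400 | 0.126 | 59.7% | 88.3% |

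**Step 3: what a position term recovers.** Simulation, 4,000 trials per scenario (Monte Carlo SE about 0.7 points), planned versus with categorical position:

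| Scenario | 0.1 per block | 0.2 | 0.3 |
|---|---|---|---|
| Random order, stroke contrast | 77% vs 79% | 70% vs 79% | 60% vs 78% |
| Random order, GROUP x CUE | 78% vs 80% | 71% vs 81% | 60% vs 81% |
| Near-balanced four-sequence order, stroke contrast | 78% vs 79% | 74% vs 79% | 66% vs 80% |

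Gains of 0.1, 0.2 and 0.3 per block total 0.3, 0.6 and 0.9 from block 1 to block 4. If all the gain comes after block 1, a gain of 0.3 gives 75% vs 78%, and 0.6 gives 66% vs 79%.

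In the four-sequence order the position effect inflates the residual but hardly moves the estimate, so the planned test is conservative: type I error 4.1%, 2.9% and 1.6% at the three gains, instead of 5%. With random order it stays near 5% (5.3% at 0.2, 5.1% at 0.3).

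If gains vary between participants (mean 0.2, SD 0.2), power is 61% vs 69%, so the term recovers only part of the loss. If stroke participants gain 0.3 per block and controls none, GROUP x CUE power is 68% planned, 74% with common position and 79% with position by GROUP.

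**Step 4: when bias enters.** Two assumed cases, with true effect zero and results in within-participant SD units:

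- Order unbalanced, taken to the extreme of Condition 1 always first: drift of 0.2 SD per block biases Condition 3 minus 1 by +0.40 SD, because the mean position difference is 2 blocks.
- Tilt blocks carrying over into later fixed-brick blocks: a tilt block precedes Condition 1 in 2/3 of the 24 orders, so the bias is about -(2/3) x carryover. Simulated bias is -0.13 SD for carryover of 0.2 SD and -0.34 SD for 0.5 SD, even under fully random order.

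A position term does not remove the second bias. With SD 0.5 and carryover 0.25, bias was -0.162 as planned and -0.163 with position in the model.

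**Step 5: change over practice.** SOP and EOP of one condition lie in the same block. A purely additive block shift therefore cancels from SOP-to-EOP change. In simulated data sets fitted with the full mixed model, that contrast was identical with and without the position term.

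**The case against.** The strongest reply is that randomising order and fitting a standard repeated-measures model is valid when position effects are additive, so a position term is an efficiency preference rather than the repair of an error. That stands if order was truly random or balanced within group. Every magnitude here is also assumed, and the benefit is small unless practice is large: 2 points or less at gains up to 0.1 per block. With a cue effect of 0.40, planned power is still 94% at 0.2. These points set the severity; they do not remove the omission.

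A reader might go further in either of two directions.

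- *The cue contrasts are biased.* The documents do not show this. They describe neither an unbalanced order nor any carryover, and a fixed first condition would sit poorly with a pseudorandom order.
- *Bias is excluded because order was pseudorandom.* This is not supported either. The term is undefined, and tilt feedback exists only in Conditions 3 and 4, so cue-specific transfer is conceivable and would survive random ordering.

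Nor does the Rationale's expectation that patients improve with more trials establish practice across blocks. It refers to recovery after the weighting cue is introduced, which TIME within CUE already covers.

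**Conclusion.** The omission is real and worth a low-cost correction; severity is CONSIDER. Under additive drift and an order random or balanced within each group, the consequence is lost precision in CUE and GROUP x CUE, with a conservative test if order was balanced. Under the assumed SD and effect, this is 2 to 3 power points at 0.1 per block, about 10 at 0.2 and about 20 at 0.3. The last two need total practice gains of roughly two (0.6/0.28) and three (0.9/0.28) times the cue effect.

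Bias in these contrasts is possible but undetermined: it depends on how orders were assigned and on whether tilt training transfers. Hypotheses (a) and (b) are unaffected only while the position effect is purely additive. If learning saturates or fatigue builds within blocks, SOP-to-EOP change would also depend on position.

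**What to change.** 1. State how block orders were assigned, and tabulate condition by position (1 to 4) within each group from the recorded order.
2. Fit a linear mixed model with GROUP x CUE x TIME, sex and categorical block position, with random intercepts for participant and for block within participant.
3. As checks, refit with position by GROUP, and separately with a term for a preceding tilt-cue block (or compare first blocks only). Block position alone does not handle cue-specific carryover. Report whether the CUE and GROUP x CUE contrasts change.
4. The document is largely in the past tense, with 79 participants included. If the data are already analysed, label this post hoc and show it beside the planned model, not in place of it.

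Cost: block order must have been recorded. Position uses 3 degrees of freedom, about 0 to 1 power point if there is no practice effect. Position by GROUP uses 6, about 0 to 1.5 points. A first-block-only comparison discards three quarters of the blocks and turns a within-participant contrast into a between-participant one, so it serves as a check only.

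### The predicted feedback-by-weighting interaction and the practice changes in stroke survivors are not tested by any term of the stated model, although all are estimable from it

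*Combined protocol and SAP*

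**What the plan says.** The Specific Aim is to "Determine the immediate effects of perceptual cues on bimanual coordination in stroke survivors". Hypothesis (a) predicts that the tilt cue shortens the time lag and raises CCr with practice. Hypothesis (b) predicts that both cues together may impair coordination at first and that it then improves.

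The Statistical plan analyses each transformed outcome by GROUP (stroke, controls), "4 PERCEPTUAL CUE CONDITIONS (veridical, coordination, altered gain, and combined coordination+ altered gain feedback", and TIME (SOP, EOP), with sex as covariate. It adds: "The focus of this study was to compare the effects of different perceptual cues on individuals with stroke and age-matched neurotypical controls". It names no contrast, simple effect or multiplicity rule.

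The next paragraph, Expected results and interpretation, says: "We expected to observe a significant group main effect and a significant interaction between feedback and arm weighting". It gives the pattern. "When the brick is fixed, we expect that there will be no difference in the arm weighting conditions"; with the brick free to tilt, "50-50 arm weighting will result in better temporal and spatial coordination compared to 70-30 arm weighting".

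Under Procedure, Condition 2 is "similar Condition 1 (virtual brick fixed in no-tilt), but the arm weighting will be such that the gain of the paretic arm was reduced", with no figure. Condition 4 refers back to Condition 2 for its reduced paretic gain and says that with "the lower gain the paretic arm contributed to ~60-70% of the virtual brick movement".

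**The concern.** The prediction is about two factors, feedback (brick fixed or free) and arm weighting (equal or altered). Neither is a factor in the model; both sit inside one four-level cue factor. The cue test asks whether any of the four condition means differ, which is a different question.

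The practice hypotheses have a similar gap. TIME averages over groups and conditions. CUE × TIME asks whether change differs between conditions, averaged over groups. Terms with GROUP ask whether stroke and controls differ. None of these says whether stroke survivors improved under the tilt cue or under both cues.

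At stake is how the results are read. A significant cue effect is compatible with no interaction at all. A significant TIME or GROUP term leaves (a) and (b) open. The choice of follow-up comparison, across four conditions, two groups, two time points and two outcomes, is left unstated.

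**Working it through.** The plan gives no alpha, effect size or power, so there is no design figure to reproduce. The group sizes are consistent: 50 + 29 = 79. Two-sided alpha 0.05, sphericity, no covariate and all effect sizes are assumptions.

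**1. The conditions as a 2×2.** C1 is fixed/equal, C2 fixed/altered, C3 free/equal, C4 free/altered. The contrasts over (C1, C2, C3, C4) are:
- tilt: (−1, −1, +1, +1)
- weighting: (−1, +1, −1, +1)
- interaction: (+1, −1, −1, +1), which is (C1−C2)−(C3−C4)

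They are mutually orthogonal and together exhaust the 3 df of the cue factor.

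**2. What the cue test picks up.** The sum of squares for each contrast is (c·m)²/4.

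| Condition means | Tilt | Weighting | Interaction | Total |
|---|---|---|---|---|
| Tilt only (0, 0, 1, 1) | 1 | 0 | 0 | 1 |
| Weighting only (0, −1, 0, −1) | 0 | 1 | 0 | 1 |
| One form of the predicted pattern (0, 0, 1, 0) | 0.25 | 0.25 | 0.25 | 0.75 |

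The first two rows give a non-zero cue effect with exactly zero interaction. In the third, one third of the cue signal is interaction. This step needs no effect-size assumption.

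**3. Illustrative size, tilt only.** Let d be the mean of the unit-length tilt contrast in SDs. Use a noncentral F(3, 231) with noncentrality n·d², where n is 79, or 4/(1/50 + 1/29) = 73.4 if the two groups are weighted equally. The cue test rejects 27–28% at d = 0.2, 55–59% at 0.3, 82–85% at 0.4 and 96–97% at 0.5. The 1-df interaction test rejects 5% throughout.

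**4. Power under the plan's own pattern.** If C1 = C2 and C3 > C4, the weighting and interaction contrasts are equal in size, so the cue noncentrality is at least twice that of the interaction. With n = 73.4, at d = 0.30 the interaction test has 72% power and the cue test at least 87%; at d = 0.33, 80% and at least 93%. The cue test is therefore not the weaker test; it is the less specific one.

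**5. Practice change.** Take an EOP−SOP change in one condition of 0.4 SD in stroke and x in controls, on 77 df. Since √(1/50 + 1/29) = 0.2334, the noncentrality is (0.4 + x)/0.2334 for the average over groups, (0.4 − x)/0.2334 for the group difference, and 0.4·√50 = 2.83 within stroke.

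| Control change x | Average over groups | Group difference | Within stroke |
|---|---|---|---|
| 0 | 39.5% | 39.5% | 79.8% |
| 0.2 | 71.9% | 13.5% | 79.8% |
| 0.3 | 84.2% | 7.1% | 79.8% |
| 0.4 | 92.3% | 5.0% | 79.8% |

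If controls improve too, the group difference says little about whether stroke survivors improved. If they do not, averaging dilutes the stroke effect.

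**6. Attribution to the cue.** If practice helps equally in Conditions 1 and 3 and the tilt cue adds nothing, a within-stroke test of the Condition 3 change still rejects about 80% at 0.4 SD. Its difference from the Condition 1 change rejects about 5% (simulation, 40,000 runs, changes correlated 0 and 0.5).

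**The case against.** Every quantity here is estimable from the stated model, and simple-effect follow-ups to a factorial model are routine. That stands: this is a gap between prediction and analysis, not a design that cannot answer the question. A reader might infer that the omnibus test costs power; under the plan's own pattern it does not. A reader might also infer that the plan would take a significant cue effect as proof of the interaction. The documents nowhere say so.

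The expected-results paragraph does name both component comparisons in words, C1 with C2 and C3 with C4. That tells the reader what to look for. But one non-significant and one significant comparison do not test the difference between them, and nothing links the paragraph to a model term.

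The interaction is an expected result rather than one of hypotheses (a) and (b), and those hypotheses do not themselves say within stroke. The within-stroke reading rests on the aim. The stated focus on stroke and controls is served by the GROUP interactions, which should stay.

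It is tempting to argue that Conditions 2 and 4 used different gains, so that the 2×2 fails. The documents do not support that. Condition 4's description points back to Condition 2, and 70-30 lies within the stated range for Condition 4. The missing figure in Condition 2 calls for clarification and is not evidence of a mismatch.

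Hypothesis (a) names no comparator, so the comparison with Condition 1 goes beyond its wording. It is needed only if improvement is to be attributed to the tilt cue.

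**Conclusion.** The concern holds as a should-fix, with medium confidence. The stated analysis contains no term that tests the predicted feedback-by-weighting interaction, and none that tests practice change in stroke survivors under the tilt cue or both cues. The first part follows from contrast algebra and needs no assumed effect size. The second depends on reading (a) and (b) with the aim. The size lies in interpretation: with a tilt effect of 0.4 SD and no interaction, the cue test would be significant in roughly five trials out of six. No figure in the documents is shown to be wrong.

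**What to change.** - Code the cue factor as TILT (fixed, free) × WEIGHTING (equal, altered), crossed with GROUP and TIME. Test the 1-df contrast (C1−C2)−(C3−C4). Report it within stroke as well as by GROUP, so that it is not itself only an average over groups, and at SOP and EOP as well as averaged, because (b) expects a transient deficit.
- From the same model, report the within-stroke EOP−SOP change in Condition 3 and in Condition 4. Before attributing the Condition 3 improvement to the tilt cue, report its difference from the Condition 1 change.
- Keep the GROUP interactions for the stroke-versus-control focus.
- Label any contrast chosen after data review as post hoc. Recruitment is complete, so that label may apply to all of them.
- Reconcile the statements on weighting (no figure in Condition 2, a range in Condition 4, 70-30 in Expected results). Reconcile or remove the parallel-versus-mirror expectation, which matches none of Conditions 1–4.

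The cost is recoding and wording, on the same data and the same 3 df. Several contrasts replace one omnibus test, so power falls if they are adjusted for multiplicity. The documents define no family of tests. As illustrations, within-stroke power for a 0.4 SD change falls from 80% to 61% at 0.05/4 = 0.0125 (two practice changes on two outcomes) and to 51% at 0.05/8 = 0.00625 (the interaction and three practice contrasts on two outcomes). For a 0.4 SD difference between the Condition 3 and Condition 1 changes, unadjusted power is 51% to 80% if the two changes correlate 0 to 0.5, and 22% to 51% at 0.00625.
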